#### 2. Background

*Briefly discuss the important literature relevant to the trial and that provides background for the trial. Include the importance of the trial and any relevant treatment issues or controversies.*

Poor adherence to prescribed medications is a major public health problem across chronic illness such as (SMI), cardiovascular disease, diabetes, and COPD and has been called “America’s other drug problem” by the National Council on Patient Information and Education. Data support that poor adherence leads to increased risk of hospitalizations, and poor recovery outcomes. In SMI, a gap as short as 10 days in which medication is not available to the individual has been associated with a two-fold increase in hospitalization. Up to \$300 billion of avoidable health care costs have been attributed to nonadherence in the US annually, representing 10% of total US health care costs. **Problem adherence is arguably one of the most important modifiable risk factors leading to poor outcomes in multiple chronic medical conditions.** In fact, according to the World Health Organization, “increasing adherence may have a greater effect on health than any improvement in specific medical treatments.” In SMI, we know that problem adherence contributes to a wide variety of poor outcomes including symptom exacerbation, hospitalization, suicide, homelessness, victimization, and unemployment. A primarily remotely delivered workable adherence intervention used by managed care is the low-hanging fruit in improving outcomes across multiple conditions. If successful, a remote, easy to deliver intervention such as R-CAT in managed care has the potential to improve adherence and outcomes for those with SMI and other chronic medical conditions and to substantially reduce the costs of care. It is important to learn about preferences satisfaction, and follow-through for remote versus home-delivered CAT. This will allow managed care and treatment organizations to determine which approach may fit best for the individuals they serve.

#### 3. Objectives and Endpoints *All data points collected in the study should support an objective or have a regulatory purpose.*

*Complete the table – add rows as needed.*

3.1. Objective(s) Clearly and concisely define the primary and secondary outcomes.	3.2. Endpoint Clearly define the endpoints. (endpoints are the basis for concluding that the objective has been met).	3.3. Justification for Endpoint Briefly explain why the endpoint(s) were chosen.
Aim 1: Examine the reach and acceptance of R-CAT and CAT for MCO members meeting entry criteria. Barriers and facilitators for initial acceptance and those identified during treatment as well as treatment satisfaction, rates of dropout and reasons for dropout will be examined.	Descriptive qualitative data regarding barriers / facilitators to initial acceptance;  Proportion of drop out	Pilot data to inform future trials and community adoption of interventions  Pilot data to inform future trials and community adoption of interventions

Aim 2: Examine pre-implementation parameters of CAT and R-CAT including case load differences for full time staff, provider and MCO assessment of barriers and facilitators and treatment related costs.	Cost of treatment including mail, supports, provider time in visit, prep time, mileage.	Pilot data to inform future trials and community adoption of interventions
Aim 3: Examine preliminary efficacy of R-CAT. We hypothesize that both CAT and R-CAT will improve adherence to medication over time and that changes within each group will be of similar magnitude. We expect increases over time in automaticity/habit strength and decreases in the overall level of psychiatric symptomatology.	Descriptive qualitative data regarding barriers and facilitators from provider perspective Pill count percent (primary) Medication possession Ratio from prescription refill data Automaticity subscale score on self-reported habit index Symptoms rated from the BPRS	Pilot data on efficacy Pilot data on efficacy Pilot data on mechanism of action Pilot data on efficacy

#### 4. Rationale

*Briefly state the reason for conducting the clinical trial.*

Cognitive Adaptation Training (CAT) is an evidence-based psychosocial treatment using environmental supports such as signs, alarms, pill containers, and the organization of belongings established in a person's home on weekly visits to cue adaptive behaviors and establish healthy habits. We have demonstrated that CAT improves adherence and outcomes for individuals with SMI. Improved adherence with CAT is maintained for at least 6 months following treatment discontinuation, suggesting that environmental supports lead to habit-formation. In response to PA-18-722 Improving Patient Adherence to Treatment and Prevention Regimens to Promote Health, we propose an R56 to collect pilot data on the delivery of a remote intervention based upon CAT—Remote-CAT (R-CAT) for improving medication follow-through. We found a telephone/mail adaptation of CAT improved both automaticity and medication adherence. Habit-strength/automaticity—the proposed mechanism of action for CAT and R-CAT—is based upon dual process theory which distinguishes controlled processes, those under the person's awareness, intention, and conscious control, from automatic processes which occur outside of the person's awareness, and are highly efficient, and minimally labor intensive. 95% of daily behaviors are automatic; but few adherence interventions target habit-formation in a systematic way. Automatic processes rely less on the resources that are known to be impaired in SMI including memory, problem-solving and motivation. The proposed mechanism of action has not been tested.

We will use components of the Reach, Effectiveness, Adoption, Implementation, Maintenance (RE-AIM) framework to compare Cognitive Adaptation Training (CAT) to Remotely delivered Cognitive Adaptation Training (R-CAT) 1-9 within a managed care organization (MCO), targeting members with serious mental illness (SMI) needing assistance with the regular taking of medication. In Part 1 of the research, **to assess both pre-implementation parameters and potential effectiveness, we will survey approximately 200-400 MCO members identified as having difficulty with medication follow through. CAT or R-CAT will be described in a randomized way and asked about acceptance, participants will then be told about the other intervention and asked about acceptance. Participants will then rate a series of statements covering dimensions of these treatments on the extent to which they agree/disagree with each statement. After the survey, participants will be offered the opportunity to participate in a research study examining CAT and R-CAT. Those who prefer one treatment over the other will get that**

treatment and those with no preference will be randomized 1:1 to CAT or R-CAT. This procedure will be followed and then altered as needed until 50 have accepted or been randomized to each group. Treatment will be offered for 6 months. In R-CAT interventions will be delivered primarily by remote and electronic means. Medication follow-through will be assessed using monthly unannounced pill counts. Automaticity (Habit formation), treatment satisfaction, barriers and facilitators to treatment and psychiatric symptoms will be assessed at baseline and every other month. Costs of providing CAT and R-CAT will be recorded including driving time, assisting with technology use, shipping, mileage, time in direct contact with member, time preparing for visits, and supports provided. Outcomes will be evaluated using within group repeated measures analyses. In sum, we are proposing to assess acceptability, feasibility, treatment satisfaction, pre-implementation parameters such as caseloads and costs, and preliminary efficacy of R-CAT compared to traditional home-delivered CAT.

**Rationale for home visits.** Home visits are required for CAT intervention, in order to deliver its treatment components and complete treatment assessment. This is the primary variable for the study, which nearly half of items rated are observational in nature (e.g. blunted affect). We have attached the SOP for home visits to protect both participants and UT staff during COVID-19 pandemic.

**Special considerations for COVID-19:** Due to the current pandemic, the CAT treatment group start date may be delayed until a time it is safe for UT staff to resume participant home visits. In the event pandemic safety precautions lead to a continued delay, additional remote treatment data may be collected and compared to historical CAT data in order to meet grant aims. [An amendment will be submitted to the IRB and approval will be sought prior to implementation, should this change be necessary.]

## 5. Study Design

5.1. Number of Groups/Arms		2	Group name(s)	Remote Cognitive Adaptation Training (R-CAT) Cognitive Adaptation Training (CAT)								
5.2. Overall Design Select all applicable												
	Randomization		Cluster Randomized									
	Group-Sequential		Adaptive Design									
	Parallel Design		Placebo-Controlled									
	Superiority		Equivalence		Non-inferiority							
Device		Pilot		Pivotal		Post-Approval						
Drug/Biologic		Phase 1		Phase 1/2		Phase 2		Phase 2/3		Phase 3		Phase 4
	Dose escalation	If yes, details →										
	Dose ranging	If yes, details →										
	Sub-studies	If yes, details →										

## 5.3. Other Design Details:

We will use components of the Reach, Effectiveness, Adoption, Implementation, Maintenance (RE-AIM) framework to compare R-CAT to home-delivered CAT. To assess both pre-implementation parameters and potential effectiveness, we will offer CAT or R-CAT in a randomized fashion to approximately 200-400 MCO members identified as having difficulty with medication follow through. CAT or R-CAT will be offered as an add on to the treatment they receive from community providers. Following baseline assessment, 100 MCO members will choose or be randomized to CAT or R-CAT for a 6-month period. Medication adherence will be assessed using monthly unannounced pill counts and claims data. Service use and costs will be obtained from the MCO. Automaticity (Habit formation) and symptomatology will be assessed monthly during treatment and follow-up.

## 6. Study Population

6.1. Study Population(s) Label/Name  To add more populations – select a row, copy & paste	6.2. Identify the criteria for inclusion The criteria that every potential participant must satisfy, to qualify for study entry.  All individuals in this study population must meet all of the inclusion criteria in order to be eligible to participate in the study	6.3. Identify the criteria for exclusion The characteristics that make an individual ineligible for study participation.  All individuals in this study population meeting any of the exclusion criteria at baseline will be excluded from study participation.
Serious Mental illness (Major Depressive Disorder, Bipolar Disorder, Schizophrenia/Schizoaffective Disorder)	1. Able to give informed consent. 2. Between the ages of 18 and 65. 3. Clinical Diagnosis of Major Depressive Disorder, Bipolar disorder, Schizophrenia, or Schizoaffective Disorder 4. Receiving treatment with oral psychiatric medications. 5. Have had a hospitalization or emergency department visit in the past year 6. Have a Medication Possession Ratio (MPR) based upon electronic refill data below 80% at least 1 of the past 4 quarters with at least 1 psychiatric medication 7. Responsible for taking their own medications 8. Report on telephone prescreen call with researcher team that they have missed at least 2 doses of medication in the past 3 weeks, that they are willing to take medication and would like remote assistance to take medication more regularly 9. Report on telephone prescreen call with research team that they have a stable living environment (individual apartment, family home, board and care facility) within the last three months and no plans to move in the next year 10. Report on prescreen research call with research team that they have no plans to change their MCO in the next 12 months 11. Have a working smart phone 12. Able to understand and complete rating scales and assessments. 13. Agree to home visits for intervention and to count pills and conduct assessments	1. Substance dependence within the past 2 months 2. Currently being treated by an ACT team 3. Documented history of violence or threatening behavior on initial assessment 4. Receive home visits to assist with medication adherence 5. Unable to complete baseline assessments
6.4. Will screen failures be allowed to re-screen at a later date?	 No  Yes If yes, describe criteria below ↓	
	We will re-screen when they initiate a follow-up call or we will call them in 3 months.	

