## 7. Study Intervention(s) being tested or evaluated

*This can include prevention, diagnostic or therapeutic interventions (e.g., drug or device) or educational, health services or basic science interventions (e.g., educational program, health care delivery model, or examining basic physiology)*

**Cognitive Adaptation Training (CAT) (completed at baseline and once weekly for 6 months or until study completion; when allowable).**

Individuals choosing or assigned to CAT will continue to see all their current treatment providers and have CAT as an added service. CAT is a manual-driven, evidence based psychosocial treatment developed to bypass impairments in controlled

processes such as directed attention, problem solving, memory and motivation which often characterize individuals with SMI. CAT uses environmental supports such as signs, calendars, alarms, pill containers, and checklists to cue and sequence adaptive behaviors such as taking medication, socializing with others, and taking care of independent living skills. CAT environmental supports are established and maintained on weekly home visits. CAT has been disseminated to multiple countries and is a billable service for many community mental health centers in the U.S.

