**Part 1:**

Telephone interviews: based upon a list provided by Superior Medicaid as possibly meeting inclusion criteria for the pilot study, the research team will call individuals to invite them to participate in a telephone interview. Verbal consent will be obtained from those interested in participating, and the interviews will be recorded over the phone. The interview will involve the researcher describing the R-CAT and CAT programs and after a description of each, participants will be asked a series of questions to assess their attitudes and acceptance of each program. Those who complete the telephone interview will be informed about the clinical trial (Part 2) and will undergo a general screening (described below) if interested.

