**Part 2:**

**Telephone Pre-screening (screening visit)** - based upon a list from superior Medicaid we will call individuals to determine whether they meet inclusion criteria outlined above and ask them about their interest in participating. **Diagnosis.** Will be based upon the clinical diagnosis (DSM-5) of the treating prescriber. This is done to improve ease of implementation in health maintenance organizations.

**Acceptability/Feasibility (ongoing)** - will be based upon numbers of individuals accepting initial offers of CAT or R-CAT, numbers with and without preferences for either treatment, and reasons for choosing / not choosing one add on treatment versus another. In addition, we will examine drop-out rates by treatment group and reasons for drop out. Barriers and facilitators to the selected or assigned treatment and treatment satisfaction will be queried at routine assessments.

**Symptomatology (baseline and at Months 2, 4 and 6)** - Symptoms will be assessed by a trained rater using the Brief Psychiatric Rating Scale-Expanded version. A total score reflects an overall level of symptomatology. (20 minutes).

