### 12.2. Sample Size Determination

Include number of participants to recruit, screen, and enroll to have adequate power to test the key hypotheses for the study. Provide all information needed to validate your calculations and judge the feasibility of enrolling and following the necessary number of participants.

This is a pilot study and not powered for testing efficacy. Given that, we examined power for proportions using PASS (Aims 1 and 2). We will approach a minimum of 200 individuals to examine the acceptance rates of an initial offer of CAT versus R-CAT. We will be able to detect a 20% difference in proportions in acceptance with a power greater than .80; two-tailed alpha =0.05. We don't expect dropout rates to vary greatly between the 2 treatments but with 100 individuals and 50 in each of 2 treatment groups we will be able to detect a difference in drop out of at least 10% versus 30% at a power of .80; alpha=0.05. A smaller difference in dropout across 6 months would not be likely to impact decisions about which treatment to adopt and is not important to detect. Aim 3 examines differences from baseline within 4 groups (those with a preference for CAT; those with a preference for R-RCAT; those with no preference randomized to CAT and those with no preference randomized to R-CAT). With 25 per group for the randomized samples within each treatment SAS Power indicates that the smallest detectable effect would be for pill count adherence going from 70% to 85%. We would have power of .80 to detect difference of about 25% in pill count adherence proportions that that correlate .48 with probabilities of adherence from 60-85% in with a one tailed test at alpha of .05. <http://statulator.com/SampleSize/ss2PP.html>. This was verified using a simulation using 5000 replications. A one-tailed test is used as we are not interested in whether the intervention makes adherence worse.

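### Inclusion criterion 8 makes wanting remote help a condition of entry, so members who want only home-delivered CAT cannot join the CAT-preference group

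*Combined protocol and SAP*

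**What the plan says.** Section 6.2 lists a single study population, and its heading says that individuals must meet all "of the inclusion criteria in order to be eligible to participate in the study". Criterion 8 is answered on the prescreen call. Besides recent missed doses, the member must report "that they are willing to take medication and would like remote assistance to take medication more regularly". There is no alternative for home-delivered help and no version specific to an arm. Criterion 13 requires agreement to home visits for three purposes: intervention, pill counts and assessments.

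Section 8.6 places this screen after the Part 1 interview: those who complete the interview "will be informed about the clinical trial (Part 2) and will undergo a general screening" if interested. For the Part 2 prescreen it states that "we will call individuals to determine whether they meet inclusion criteria outlined above".

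Allocation is partly by choice. Section 4 says "Those who prefer one treatment over the other will get that" treatment, with 1:1 randomization for those without a preference. Section 5.3 says "100 MCO members will choose or be randomized to CAT or R-CAT for a 6-month period". Section 7 says of the home-delivered treatment that "CAT environmental supports are established and maintained on weekly home visits", and describes R-CAT as the remote version.

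Section 12.2 names four Aim 3 groups, starting with "those with a preference for CAT; those with a preference for R-RCAT", followed by the two randomized groups. Section 12.4 follows the trajectories of all four. Under Aim 1 it also analyses dropout and satisfaction with self-selected and randomized members both pooled and apart.

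**The concern.** The difference between the two treatments is whether help comes remotely or at home. Criterion 8 makes a wish for the remote kind a condition of entry for everyone, including those who will choose the home kind. The members with the firmest preference for home delivery, who want no remote help at all, are the ones it turns away.

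Section 2 says the trial is meant to show how preference, satisfaction and follow-through differ between remote and home delivery, so that organizations can decide what fits their members. People who want only home delivery belong to that question. If they cannot enter, the dropout, satisfaction and adherence results of the CAT-preference group do not describe them, and a reader of the report would not see this from the group's label.

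**Working it through.** The plan gives no figure to reproduce here, so the check sets the rules side by side and follows each kind of member through them.

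**Inputs.** All criteria must be met (Section 6.2). Criterion 8: would like remote assistance. Criterion 13: agrees to home visits for intervention, pill counts and assessments. Members with a preference receive the treatment they prefer (Section 4). CAT is delivered at home and R-CAT remotely (Section 7).

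| Member | Criterion 8 | Criterion 13 | Enters? | Aim 3 group |
|---|---|---|---|---|
| Wants home-delivered help, no remote help | Fails | Meets | No | Would have been CAT preference |
| Prefers CAT, would also like remote help | Meets | Meets | Yes | CAT preference |
| Prefers R-CAT, accepts home visits for all three purposes | Meets | Meets | Yes | R-CAT preference |
| Prefers R-CAT, refuses home visits for intervention | Meets | Fails | No | Would have been R-CAT preference |
| No preference, content with either | Meets | Meets | Yes | Randomized |

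**Step 1.** The first row shows the conflict. Nothing in Sections 4, 5.3, 7, 8.6 or 12 waives criterion 8 for members who choose CAT.

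**Step 2.** The fourth row shows that criterion 13, read just as literally, removes some R-CAT choosers. Both preference groups are therefore narrowed, and those who enter are open to both modes.

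**Step 3.** The two criteria differ in the support they have elsewhere. Home visits serve both arms: Section 8.6 schedules in-home pill counts at months 0, 2, 4 and 6, and Section 7 allows occasional home visits in R-CAT, expected for no more than 5-10% of individuals. For criterion 8 no section says why someone choosing CAT must want remote help. The video pill counts at months 1, 3 and 5 are assessment rather than assistance, and criterion 11 already requires a smart phone.

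**Step 4.** Part 1 acceptance and stated preference are recorded in the interview before the general screening, so criterion 8 does not directly restrict them. The Aim 1 dropout and satisfaction comparisons use Part 2 participants, so it does reach those.

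**Step 5.** The share of CAT choosers who want no remote help is not given, nor is how they would differ in outcome. Neither the number excluded nor the resulting distortion can be calculated. The extent is 1 of 4 Aim 3 groups.

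**The case against.** The strongest reply is that the trial may reasonably want members who are open to both modes. Members without a preference are randomized, every participant has video counts and needs a smart phone, CAT is offered only when allowable, and the COVID-19 paragraph in Section 4 foresees delayed home visits and extra remote data. The criterion also says that the member would like remote help, not that they prefer it.

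Part of this stands. CAT choosers who would also like remote help do enter, so the group is narrowed and not closed. But no section states openness to both modes as a requirement or gives it as the reason for criterion 8. A member who chooses CAT is never randomized to R-CAT. The COVID-19 paragraph makes its change conditional on a later amendment and does not move CAT choosers to remote treatment.

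A second reply concerns size. Section 4 plans 50 per treatment and Section 12.2 has 25 per randomized group, leaving about 50 - 25 = 25 CAT choosers. At an assumed dropout of 20%, the standard error is sqrt(0.2 x 0.8 / 25) = 8 points, a 95% half-width of about 1.96 x 8 = 16 points. At 10% and 30% the half-widths are about 12 and 18. A modest shift from selection would be lost in that imprecision. This supports a low rating, but it does not change whom the group represents.

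A reader might also infer that the filter is one-sided, so that the planned baseline comparison sets a filtered CAT group against an unfiltered R-CAT group. The documents do not support that, because criterion 13 filters R-CAT choosers as well.

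**Conclusion.** The point holds and is minor. On a literal reading of Section 6.2, a member who wants home-delivered help and no remote help is ineligible, although Sections 4, 5.3, 7, 12.2 and 12.4 provide for a group that chooses CAT. Results for that group would apply only to CAT choosers who also want remote help.

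Three stronger conclusions do not follow. The CAT-preference group is not impossible to fill. The Part 1 acceptance and preference rates are not directly distorted. No figure can be put on bias in dropout: the 10% versus 30% contrast in Section 12.2 is between treatments and says nothing about differences among CAT choosers.

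The conclusion assumes that the prescreen applies the written words. If staff already ignore *remote*, practice departs from the written rule and the text still needs correcting. Whether anyone has been turned away on this ground is not stated.

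**What to change.** Delete *remote* from criterion 8 and from the prescreen script, so that the member need only want help to take medication more regularly. For anyone already screened, record which wording applied.

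Review criterion 13 in the same amendment. Keep agreement to home visits for pill counts and assessments. For the words *for intervention* there are two consistent options:

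- keep them, because R-CAT may occasionally need a home visit, and report that the results apply only to members who accept home visits; or
- limit them to members who may receive CAT.

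The amendment should not claim that eligibility has become independent of delivery mode. Home visits for counts and assessments remain compulsory, and under the first option so does agreement to home visits for intervention.

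The cost is a short protocol amendment and a matching change to the script. No measurement, sample size or analysis changes: criterion 11 and the video counts stay, members who choose R-CAT show their wish for remote help by choosing it, and those without a preference accept either mode.
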